12 DATA MANAGEMENT AND QUALITY CONTROL

The complete dataset will be collected for all patients who are randomised into the trial. If consent to participate is withdrawn then any data collected will be retained and used in the study, with no further data collected or study procedures carried out on the patient. The electronic data capture system, InForm will be used to document clinical data.

The signed, original informed consent forms and the documentation of all study procedures and assessments will be kept in the patients' study notes. All data to be transferred to the study co-ordination centre with all appropriate supporting documentation will be done as required such as hospital reports or imaging reports with all patient identifiers removed. Patients study documents will be identified by their study-specific patient number allocated at randomisation.

12.1 Electronic Recording of data

(Electronic CRF): The principal means of data collection from patient visits will be Electronic Data Capture (EDC) via the internet (InForm). Data is entered into the EDC system via site personnel. All data recorded in the CRF will be signed by the Investigator or his/her appropriate designee. All changes made following the electronic signing will have an electronic audit trail with a signature and date. Specific instructions and further details will be outlined in SOPs and/or manuals.

12.2 Risk Assessment

A study-specific risk assessment will be performed prior to the start of the study to assign a risk category of 'low', 'medium' or 'high' to the trial. Risk assessment will be carried out by the ICTU QA Manager in collaboration with the Study Manager and the result will be used to guide the monitoring plan. The risk assessment will consider all aspects of the study and will be updated as required during the course of the study.

12.3 Monitoring

The trial conduct will be monitored and by Imperial Clinical Trials Unit (ICTU), in accordance with the trial risk assessment and monitoring plan. Further details of level of monitoring to be performed will be provided to study sites in the Investigator Site File. The monitor will assess compliance with the protocol, GCP and regulatory requirements. They will also review the patient consenting process, essential study documents, AE and SAE reporting as well as verifying source data to ensure the quality, accuracy and validity of the data at each investigational site.

12.4 Quality Control and Quality Assurance

Quality Control will be performed according to ICTU internal procedures. The study may be audited by a Quality Assurance representative of the Sponsor. All necessary data and documents will be made available for inspection.

12.5 Archiving

Data and all appropriate documentation will be stored for a minimum of 10 years after the completion of the study, defined as the last patient's last visit. Local investigator sites will be responsible for making arrangements for the secure archiving of study documents locally.

13 ETHICAL and LEGAL ISSUES

13.1 Ethics Approval

Ethics approval has been granted by the NRES Committee London - Brent to conduct the study in the United Kingdom. The study must be submitted for Site Specific Assessment (SSA) at each participating NHS Trust. ICTU will require a copy of the Trust R&D approval letter before participants can be entered into the study.

The study will be conducted in accordance with the recommendations for physicians involved in research on human subjects adopted by the 18th World Medical Assembly, Helsinki 1964 and later versions.

13.2 Consent

Consent to enter the study must be sought from each participant only after a full explanation has been given, an information sheet offered and time allowed for consideration. Signed participant consent must be obtained. The right of the participant to refuse to participate without giving reasons must be respected. After the participant has entered the study the clinician remains free to give alternative treatment to that specified in the protocol at any stage if he/she feels it is in the participant's best interest, but the reasons for doing so must be recorded. In these cases, the participants remain in the study for the purposes of follow-up and data analysis. All participants are free to withdraw at any time from the protocol treatment without giving reasons and without prejudicing further treatment.

13.3 Confidentiality

The investigator must ensure that the subject's confidentiality is maintained. On the CRF or other documents submitted to the Sponsors, subjects will be identified by a subject ID number only. Documents that are not submitted to the Sponsor (e.g., signed informed consent form) should be kept in a strictly confidential file by the investigator. The investigator shall permit direct access to subjects' records and source document for the purposes of monitoring, auditing, or inspection by the Sponsor, authorised representatives of the Sponsor and RECs

13.4 Indemnity

Imperial College London holds negligent harm and non-negligent harm insurance policies which apply to this study.

13.5 Sponsor

Imperial College Academic Health Science Centre will act as the main Sponsor for this study. Delegated responsibilities will be assigned to the Investigational Centres taking part in the study.

13.6 Funding

Medtronic and British Heart Foundation (BHF) are providing the funding for this study in the form of a grant.

14 STUDY MANAGEMENT STRUCTURE

14.1 Trial Steering Committee (TSC)

A Trial Steering Committee consisting of an Independent Chair (i.e. an individual with experience in clinical research who is not part of the trial team), Chief Investigator, Independent Experts, Operations Manager, Trial Manager and representatives of the funders is convened. The TSC will be responsible for the scientific and ethical conduct of the study and will supervise progress of the trial. The trial protocol and subsequent amendments will be approved by the TSC. The TSC members will be required to attend TSC meetings which will be held prior to the start of the trial and as required throughout the trial.

14.2 Data & Safety Monitoring Board (DSMB)

An independent Data & Safety Monitoring Board (DSMB) will be convened and meet to provide independent advice on study conduct and safety issues. The DSMB will meet at the start of the trial and as required thereafter based on planned interim analyses. Meetings will be held approximately annually or as required throughout the duration of the trial. Safety data will be studied after 75 and 150 patients have received treatment, or one year after the first patient is randomised, whichever occurs sooner. Meetings will also be held as necessary should any urgent issues occur. The DSMB will develop a charter which describes the framework within which it will operate.

14.3 Early Discontinuation of the Study or Individual Subjects

14.3.1 Early Discontinuation of the Study by Data Safety Monitoring Board (DSMB)

If, in the opinion of the DSMB the clinical observations in the study suggest that it might not be justifiable to continue, the study may be terminated following consultation with the Sponsor and the TSC. Alternatively, the Sponsor may give written notification to the investigator, Ethics Committee of the early discontinuation of the study, including reasons.

In case of early discontinuation of the study, the next Follow-up Visit assessment should be performed for each subject, as far as possible. The patient will then be returned to the treating secondary care team.

14.3.2 Early Discontinuation of Individual Subjects

The reason for a patient discontinuing study will be recorded in the case record form. A discontinuation occurs when an enrolled patient permanently and totally withdrew the study consent regardless of the circumstances, prior to completion of the protocol. A discontinuation must be reported immediately to the co-ordinating centre. It may not be necessary for a patient to stop follow-up after an endpoint. The investigator will provide or arrange for appropriate follow-up for such patients, and document the course of the patient's

condition. The patients should, if at all possible, be followed to the end of the study despite reaching the study endpoint as the intention-to-treat analysis includes all patients. Subjects will be informed that they are free to withdraw from the study at any time and for any reason. In case of early discontinuation of a subject, the Follow-up assessments should be performed, as far as possible.

14.4 Trial Management Group (TMG)

The Trial Management Group (TMG) consisting of the Chief Investigator, Operations Manager, Trial Manager, Trial Monitor and additional members as appropriate, will meet fortnightly to ensure that the study runs smoothly and according to the pre-agreed timetable

14.5 End of trial

The trial will end when all patients have completed month 12 follow-up visit.

- g) Did you have any procedures whilst you were in hospital
If yes- what was it

ii) Have you had any of the following symptoms;

- a) racing heart beat lasting more than half an hour
if yes – <1/week or >1/week
- b) racing heart beat more than 5mins but less than half an hour
if yes – <1/week or >1/week
- c) Have you had any unexplained breathlessness, dizzy spells, chest pain, fainting attacks/weakness/confusion
if yes which-

iii) Do you think you the situation is bad enough that you need to change medication or have another procedure to help make you better? (yes/no)

**iv) Do you think you are having side effects or complications from your treatment?
(yes/no)**

v) If you have answered yes to any of the questions we recommend that you see your GP and discuss whether you need another appointment with your heart specialist. We will pass on the information from the phone call to your heart specialist and they may contact you directly if they are concerned about any of the answers you have given.

21 Appendix 2: AVATAR-AF Endpoint definitions

Symptoms of atrial fibrillation/tachycardia:	palpitations lasting >5min, transient dizziness or fainting, lethargy, shortness of breath on exertion, chest discomfort
• ECG documentation:	
• irregularly narrow QRS without p-waves lasting >30secs narrow QRS with A>V evident or 1:1 at >100bpm with sudden onset lasting >30sec or incessant at constant rate
Pericardial Effusion:	global echo-lucent space around myocardium >0.5cm maximally in diastole 
• SEVERE: pericardial drain inserted, sternotomy,• MODERATE: delayed discharge
Vascular Bleeding:	Bleeding visualised by haematoma or imaging associated with Hb drop of >2g/dl 
• SEVERE: Surgical intervention, transfusion required
Phrenic Nerve Palsy:	Reduced excursion of hemi-diaphragm on chest x-ray in inspiration and expiration more than 1day after procedure 
• SEVERE: exertional symptoms with CXR changes at >3mth• MODERATE: asymptomatic with CXR changes at >3mth
PV stenosis:	Evidence of >50 reduction in ostial PV diameter by any form of imaging. 
• SEVERE: exertional symptoms at >3mth• MODERATE: asymptomatic at >3mth
Drug Side Effect:	Symptoms that are well recognised with drug or stop after ceasing drug
Stroke:	logical symptoms/signs associated with MRI or CT evidence of neurological bleeding/ischaemia

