6.1 AVATAR-AF Ablation Protocol

Anticoagulation regime will be at physician's discretion according to established HRS/ESC guidelines guided by CHADS-VASC scoring system. Patients on anticoagulation may follow a continuous, bridging or without anticoagulation as per local protocol.

The procedure is performed under sedation or general anaesthetic according to local preference. TOE is performed according to local protocols. Femoral sheaths placed in the right femoral vein (ultrasound guidance allowed). A single transeptal puncture is performed under TOE, ICE, CS catheter or aortic pigtail guidance. If coronary sinus catheter is used, this should be performed without electrograms if possible.

Pulmonary venography taken. The sheath is exchanged for a Cryosheath or other suitable large sheath and an Arctic Front Advance balloon is used to occlude the PV to Grade 3/4 and deliver

2 x 3min cryoablations to each vein. Phrenic nerve monitoring will be done with a temporary transvenous pacing wire and box. No specialist EP catheters are deployed and no formal assessment of PVI is done. ACT kept above 300s. Reversal of heparin with Protamine is allowed.

Transthoracic Echo (hand-held echo with documentation sufficient), Hb check and groin survey at 6 hours post-procedure. If all are stable, the patient is discharged as a daycare procedure and given appropriate instructions and advice on potential concerns and process for seeking advice

Patient is given a date for possible 'redo' procedure at 10wks ± 7 days post ablation.

All medication is continued for 4 weeks post-ablation and then all agents being used for anti-arrhythmic effect are stopped.

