6.3 Conventional AF Ablation

Patients randomised to the conventional AF Ablation arm will undergo the conventional Cryoablation procedure. This arm will be used as a second control arm to compare the differences in impact on healthcare resources, complication rates and clinical outcomes between conventional ablation and AVATAR-protocol ablation.

Anticoagulation regime will be physician discretion according to established HRS/ESC guidelines guided by CHADS-VASC scoring system. Patients on anticoagulation may follow a continuous, bridging or without anticoagulation as per local protocol.

The procedure is performed under sedation or general anaesthetic according to local preference. TOE is performed according to local protocols. Femoral sheaths placed in the right

femoral vein (ultrasound guidance allowed). A single or double transeptal puncture may be done guided by TOE, aortic pigtail, ICE or CS catheter guidance. Pulmonary venography taken. The sheath is exchanged for a Cryosheath or other suitable large sheath and an Arctic Front Advance balloon is used to occlude the PV to Grade 3/4 and deliver 2 x 3min cryoablations to each vein. Phrenic nerve monitoring can be according to local protocol.

The PV will be mapped using a circular mapping catheter of the operators choice and the number of veins isolated with this approach documented. PV isolation is completed with either repeat cryoballoon, deflectable cryotherapy catheter or radiofrequency catheter. The catheters used and outcomes documented.

The patient is monitored overnight and should have an Hb, groin and echo (handheld with documentation sufficient) check prior to discharge.

All medication is continued for 4 weeks post-ablation and then all agents being used for anti-arrhythmic effect are stopped.

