6.4 Redo Ablation (10 weeks± 7 days)

Anticoagulation regime will be physician discretion according to established HRS/ESC guidelines guided by CHADSVASC scoring system. Patients on anticoagulation may follow a continuous, bridging or without anticoagulation as per local protocol.

The procedure is performed under sedation or general anaesthetic according to local preference. TOE is performed according to local protocols. Femoral sheaths placed in the right femoral vein (ultrasound guidance allowed). A single or double transeptal puncture is performed under TOE, ICE, aortic pigtail or CS catheter guidance.

Pulmonary venography taken and PV mapping performed. Further ablation can be performed according to operator preference by radiofrequency ablation, Cryoballoon or cryocatheter.

Transthoracic Echo (hand-held echo with documentation sufficient), Hb check and groin survey at 6 hours post-procedure.

Patients in AVATAR-AF protocol arm are discharged as a daycare procedure and given appropriate instructions and advice on potential concerns and process for seeking advice.

Patients in conventional ablation arm are kept overnight.

All medication being used for anti-arrhythmic effect are stopped.

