10.1 Adverse Event Definitions

Adverse Event (AE): any untoward medical occurrence in a patient or clinical study subject.

Serious Adverse Event (SAE): any untoward and unexpected medical occurrence or effect that:

- Results in death
- Is life-threatening – refers to an event in which the subject was at risk of death at the time of the even; it does not refer to an event which hypothetically might have caused death if more severe.
- Requires hospitalisation (>24 hrs), or prolongation of existing inpatient hospitalisation
- Results in persistent or significant disability or incapacity
- Is a congenital anomaly or birth defect

Medical judgement should be exercised in deciding whether an AE is serious in other situations. Important AEs that are not immediately life-threatening or do not result in death or hospitalisation but may jeopardise the subject or may require intervention to prevent one of the other outcomes listed in the definitions above, should also be considered serious.

Any Adverse Events that are related to atrial arrhythmia will be reported as endpoints rather than Adverse Events. Serious Adverse Events that are related to atrial arrhythmia must be reported as SAEs.

Any planned hospitalisations such a for a redo ablation procedure prior to entry into the Discharge protocol or planned surgery will not be reported as Serious Adverse Events as these are expected.

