8.4. Safety Variable Analysis

Adverse events will be summarised by treatment and severity. A separate table summarising adverse events and their relationship to study treatment will also be produced.

Serious adverse events will be listed and summarised by site, category and treatment. A separate table summarising serious adverse events and their relationship to study treatment will also be produced.

All safety variables will be summarized in the form of frequency tables for categorical variables or descriptive statistics for continuous variables. Quality-of-Life (QoL) questionnaire results will be summarised by Health State Score. Atrial Fibrillation Effect on QualiTy-of-life (AFEQT) questionnaire results will be summarised by both overall AFEQT score and subscale score derived using the formulae stated within the AFEQT Questionnaire Instruction and Scoring Manual

REFERENCES

If it is deemed appropriate, treatment effect will be assessed via t-test for continuous variables and Chi-square test or Fisher exact test for categorical variables (with the appropriate generalized linear model being used). Models containing one or more of the following covariates may also be assessed if deemed necessary: site, weight, hypertension, number of anti-arrhythmics taken by patient prior to 1st intervention. A p-value of 0.025 or less will be considered significant. Any testing for treatment effect will be carried out between AVATAR-AF Ablation and the Anti-Arrhythmic drug treatment arm in order to investigate the primary objective. The secondary objective will be assessed by testing AVATAR-AF Ablation against the Conventional Ablation arm.

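### The moderate grade for pericardial effusion and, on one reading, the SAE prolongation criterion depend on each ablation arm's planned stay, so the same undrained effusion can be classified differently by arm

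*Protocol*

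**What the plan says.** Appendix 2 of the protocol defines a pericardial effusion by echo: "global echo-lucent space around myocardium >0.5cm maximally in diastole". It then gives two grades. One is "SEVERE: pericardial drain inserted, sternotomy". The other is "MODERATE: delayed discharge", with no statement of what the delay is measured against.

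The planned stay depends on the arm. In AVATAR (Protocol 6.1), echo, haemoglobin and groin checks are made at 6 hours, and "If all are stable, the patient is discharged as a daycare procedure". In the conventional arm (Protocol 6.3), "The patient is monitored overnight and should have an Hb, groin and echo (handheld with documentation sufficient) check prior to discharge". At a redo (Protocol 6.4) the checks are at 6 hours in both arms, but AVATAR patients go home the same day and "Patients in conventional ablation arm are kept overnight".

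Protocol 10.1 makes an event serious if, among other things, it "Requires hospitalisation (>24 hrs), or prolongation of existing inpatient hospitalisation". Planned hospitalisations are exempt.

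Protocol 10.3 has a separate mild, moderate and severe scale, based on impairment and the need for intervention. Discharge plays no part in it.

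On reporting, SAP 8.4 states: "Adverse events will be summarised by treatment and severity". SAP Table 7.1 shows severity and reasons for SAEs by arm. SAP 7.2 defines secondary endpoint 2 as the number of, and time to, any listed complication.

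**The concern.** A severity grade compared between randomised arms should mean the same thing in each. Here one grade is defined relative to a schedule that is itself part of the randomised strategy. A stay of the same length, for the same finding, is a departure from plan in one ablation arm and the plan itself in the other.

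Protocol 6.3 says the conventional arm is there partly to compare complication rates with AVATAR, and day-care discharge is part of the strategy under test. Safety data also go to the DSMB after 75 and 150 treated patients (Protocol 14.2), when a handful of labels can colour the picture. A reader of an arm-by-arm severity or SAE table could take a difference in labelling for a difference in harm.

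**Working it through.** The plan states no figure on this point, so the check sets the definitions side by side. Take one patient in each ablation arm with an effusion above 0.5 cm, no drain, observed until next morning, then sent home well.

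1. **Does it count as a complication?** Yes in both arms. The Appendix 2 criterion is echo size, without reference to arm or discharge.
2. **Appendix 2 grade.** In AVATAR discharge was due the same day, so it is delayed and the grade is moderate. In the conventional arm the night was planned, so nothing is delayed and the grade does not apply. The redo shows this most cleanly, because both arms then have the echo at 6 hours: the same reading at the same time can lead to a different grade.
3. **Protocol 10.3 grade.** An event that needs nothing beyond monitoring, with minimal transient impairment, falls under mild. That points to mild in both arms and disagrees with Appendix 2 for the AVATAR patient. The documents do not say which scale governs.
4. **SAE status.** In the conventional arm the night was planned and prolonged nothing. In AVATAR two limbs could apply. One night need not exceed 24 hours, and the start of the 24 hours is not stated. The prolongation limb applies only if the day-care attendance is an inpatient stay, which is not stated either. The exemption for planned hospitalisations does not cover an unplanned night. The opening words of the SAE definition require the event to be unexpected, while Protocol 10.2 lists pericardial effusion among expected SAEs. An SAE in AVATAR only is thus a possible result, not a certain one.
5. **Other complications.** Vascular bleeding, phrenic nerve palsy and PV stenosis are defined and graded in Appendix 2 without reference to discharge.
6. **Effect on the tests.** SAP 7.2 and 8.3 and Tables 5.4 to 5.6 use occurrence and time of complications. No grade enters the log-rank or Cox analysis.

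**Illustrative size.** Patients per arm: 321 / 3 = 107. The documents give no effusion rate, so both factors below are assumptions.

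Expected AVATAR patients with the arm-dependent label = 107 × effusion rate × share kept one extra night without a drain.

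- Low: 107 × 0.01 × 0.25 = 0.27
- Middle: 107 × 0.03 × 0.50 = 1.6
- High: 107 × 0.05 × 1.00 = 5.35

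The same course yields 0 such labels in the conventional arm. The number of effusions counted under secondary endpoint 2 is unchanged.

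**Check times.** At the first procedure, haemoglobin and echo are read at 6 hours in AVATAR and at an unspecified hour after overnight monitoring in the conventional arm. These readings feed the effusion criterion and part of the bleeding criterion. Protocol 6.4 uses 6 hours for both arms.

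**The case against.** The strongest reply is that the grade reaches little that matters. The endpoint that is tested ignores it. No SAP table is specified for the Appendix 2 grade, and the severity columns of Table 7.1 may well be filled from the 10.3 scale, which does not refer to discharge. Day care is part of the tested strategy, so flagging its failure is a defensible choice. All of this stands, and it limits the point to the descriptive severity and SAE summaries. It does not remove the point: two scales share a word, neither is given precedence, and sites must settle the SAE question for themselves.

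A reader might go further and infer three things that the documents do not support.

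- *That the complication comparison itself is biased by the grade.* It is not, because effusions count on size in both arms.
- *That every unplanned AVATAR night is an SAE.* That is one reading of an undefined term.
- *That the 6-hour checks hide AVATAR bleeds and effusions.* Appendix 2 requires bleeding to be visualised as well as a haemoglobin fall, so a later fall alone is not an event; the endpoint list uses a different threshold, of more than 2 units. Protocol 1.1 reports audit experience that most complications, including effusion and femoral bleeding, occur within three hours, and that the rest do not present during the overnight stay. Adverse events are also collected in all arms to the last visit. A timing difference exists, but its effect is unknown and on this account probably small.

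**Conclusion.** The point holds for the Appendix 2 moderate grade for effusion, which is not comparable between the ablation arms. It holds conditionally for SAE status: only if a day-care attendance is treated as an inpatient stay that an unplanned night prolongs. It does not extend to the count of effusions, to the log-rank and Cox tests of secondary endpoint 2, or to any other Appendix 2 complication.

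Under the assumed rates, the label would fall on roughly 0.3 to 5.4 of 107 AVATAR patients. That could be visible in a table with few events, but the range rests wholly on assumption. It would be wrong to conclude that the difference in complications between the arms cannot be interpreted. What cannot be interpreted as it stands is a difference in moderate effusions under Appendix 2, or in SAEs that arise only from an unplanned night.

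**What to change.** These changes concern how events are classified and reported. They do not concern how long patients are kept or when they are examined.

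- **Grade.** For between-arm summaries, replace delayed discharge in Appendix 2 with an arm-neutral criterion. Either a common time after the procedure (the SAE definition already contains a 24-hour figure) or the 10.3 scale would serve. State which scale governs Table 7.1. Have the adjudication committee apply it, since 10.3 leaves grading to investigators who know the arm.
- **SAE status.** State in 10.1 whether an unplanned overnight stay after day care is by itself an SAE, and from when the 24 hours run. Reconcile the word unexpected in 10.1 with the list of expected SAEs in 10.2.
- **Separate report.** Tabulate unplanned overnight stays with the reason, for first and redo procedures. SAP Table 6.1 has a day-case discharge row, but it covers the first intervention only and gives no reason; the abbreviated Table 6.3 shows no such row.
- **Check times.** Reconcile 6.1, 6.3 and 6.4 for endpoint ascertainment, or time-stamp the haemoglobin and echo readings and state the difference when reporting.

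The cost is a few lines of text, one or two eCRF fields and one table. The downside is that some unplanned AVATAR nights lose the moderate or SAE label in the comparison, which is why the separate report is needed.
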